Subjects assigned to esketamine 84 mg dosing will start treatment sessions with 56 mg of intranasal esketamine on Day 1 to improve tolerability. On Day 4 (Visit 3.3), the dose will be increased to 84 mg as a forced titration and remain at 84 mg for all subsequent intranasal treatment sessions. Subjects who are randomly assigned to 28 mg and 56 mg on Day 1 will remain on that dose for all subsequent intranasal treatment sessions. No adjustment to the intranasal esketamine dose is permitted during the double-blind induction phase.

Use of benzodiazepines and non-benzodiazepine sleeping medications (eg, zolpidem, eszopiclone, and zopiclone) is prohibited within 12 hours prior to the start of each intranasal treatment session.

Responders (subjects who have $\geq 50\%$ reduction from baseline in MADRS total score) at the end of the double-blind induction phase will be eligible to proceed to the posttreatment phase; those who do not (ie, nonresponders) will proceed to the 4-week follow-up phase.

If a subject withdraws before the end of the double-blind induction phase for reasons other than withdrawal of consent, the Early Withdrawal (EW) Visit should be conducted within 1 week of the date of discontinuation, followed by a 4-week follow-up phase. MADRS information will be collected during the 4 week follow-up phase. If the EW Visit occurs on the same day as a scheduled visit, the EW Visit can be performed on the same day; duplicate assessments are not required.

Given the potential for treatment-emergent transient elevation in SBP and DBP, the guidance on Blood Pressure Monitoring (see Section 6.3.1) should be followed on intranasal dosing days during the double-blind induction phase.

Posttreatment Phase

Responders who completed the double-blind induction phase will enter the 24-week posttreatment phase to evaluate durability of efficacy after cessation of add-on intranasal esketamine or placebo treatment while continuing the oral antidepressant treatment regimen, as assessed by the time to relapse and proportion of responders and remitters at each visit in this phase. All subjects who are discontinued must be treated with an oral antidepressant after completion of the study, unless it is clinically inappropriate.

Relapse is defined as any of the following:

- MADRS total score ≥ 22 for 2 consecutive assessments. The date of the second MADRS assessment will be used for the date of relapse.

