Subjects who enter the OL induction phase will start treatment sessions with 56 mg of intranasal esketamine on the first day of OL induction phase (Day OL1). On the fourth day (Day OL4), the dose will be increased to 84 mg. On Day OL8 and OL11, the dose could be maintained, increased or reduced by 28 mg as determined by the investigator based on efficacy and tolerability. On Day OL15, a dose reduction is permitted if required for tolerability; no dose increase is permitted on Day OL15. After Day OL15, the dose should be stable (unchanged). If needed for tolerability, a dose reduction is permitted from Day OL15 until Day OL25.

The oral antidepressant medication initiated from the prospective lead-in phase, which will continue in the posttreatment phase will also be maintained throughout this phase.

[figure not shown]
Guidance on Blood Pressure Monitoring (Section 6.3.1) as indicated for intranasal treatment sessions during the double-blind induction phase should also be followed on intranasal dosing days in the OL induction phase.

Follow-up Phase

Following subjects will have follow-up Visits; subjects who withdraw from double blind induction phase, nonresponders after double-blind induction phase, responders who withdraw within 4 weeks after the last dose of double blind intranasal drug and all subjects who receive open label intranasal drug. During this phase, further clinical/standard-of-care treatment will be provided by the study investigator however, in order to better assess potential withdrawal symptoms from intranasal study drug, the oral antidepressant medication must be continued for the follow-up phase unless determined as not clinically appropriate.

A schematic representation of the study design is provided in [Figure 1](#).

Figure 1: Study 54135419TRD2005 Flowchart

Esk: esketamine; IN: intranasal; AD: Antidepressant Day 1: The first day in the double-blind induction phase.

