To improve tolerability, subjects who will be randomly assigned to esketamine 84 mg will start at 56 mg on Day 1 and then, in a blinded manner, the dose will be increased to 84 mg on Day 4. By the lower dose (56 mg) initially and then increasing to 84 mg, may allow subjects to adjust to the effects of the lower dose before going to the higher dose (84 mg). Thereafter, no dose adjustments will be permitted. For example, internal data from the CADSS suggest a dose-response, with the greatest effect seen initially on the 84 mg dose (Study ESKETINTRD2003).¹⁶ However, on subsequent repeated dosing, dissociative symptoms lessen. Starting with a lower dose may therefore limit the number of subjects discontinuing the study treatment because of intolerability in the 84-mg dose group.

Oral Antidepressant

A new, OL oral antidepressant medication will be initiated for all subjects in the prospective lead-in phase. Each subject will be assigned to receive 1 oral antidepressant medication of SSRIs, SNRIs, or mirtazapine (ie, escitalopram, paroxetine CR, sertraline, duloxetine, venlafaxine XR, or mirtazapine), that the subject has not previously had a nonresponse to in the current depressive episode, has not been previously intolerant to (lifetime).

The antidepressant medication will be assigned by the investigator based on review of the MGH-ATRQ and relevant prior antidepressant medication information.

The SSRIs and SNRIs were selected because they are the most commonly prescribed antidepressant classes in this population and are generally well tolerated. Mirtazapine was selected because >50% of Japanese subjects used mirtazapine in the Study ESKETINTRD2003.¹⁶ If clinically indicated, subjects can join the prospective lead-in phase and initiate a new oral antidepressant before discontinuation of current oral antidepressants; therefore, cross-tapering is allowed. Dosing of the oral antidepressant will begin from prospective lead-in phase. New oral antidepressant treatment should be titrated to the approved maximum dose, to optimize the potential for response. The up-titration schedule should be per prescribing information. The dose, which is above the minimum therapeutic dose defined in MGH-ATRQ should be kept at last 4 weeks during the prospective lead-in phase, in case they start at lower doses.

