depression. After 6 weeks, subjects who are nonresponders to the new oral antidepressant treatment at the end of the prospective lead-in phase can be eligible to proceed to the double-blind induction phase. Nonresponse at the end of the prospective lead-in phase is defined as $\leq 25\%$ improvement in the MADRS total score from Visits 2.1 to each of Visit 2.3 and 3.1 (prerandomization) respectively, and a MADRS total score of ≥ 28 on each of the Visits 2.1, 2.3, and 3.1 (prerandomization). Assessment of antidepressant treatment response at the end of the prospective lead-in phase will be performed by investigators. All other subjects who do not proceed to the double-blind induction phase will end study participation at this time. No follow-up or further study visits will be performed for these subjects. All subjects who are discontinued must be treated with an oral antidepressant after completion of the study, unless it is clinically inappropriate.

MADRS assessment throughout the study will be performed by an independent, remote, blinded rater. The remote MADRS interviews will be recorded to assess accuracy and thoroughness of the interviews and measure overall quality assurance.

Double-blind Induction Phase

The 4-week fixed dose double-blind induction phase will start on Day 1 and end at Day 28. A total of 183 subjects will be randomly assigned in a 2:1:1:1 ratio to receive double-blind intranasal treatment with either placebo, esketamine 28 mg, esketamine 56 mg, or esketamine 84 mg add-on to the continued stable oral antidepressant initiated in the prospective lead-in phase. The intranasal treatment sessions (esketamine or placebo) will occur twice weekly. Subjects will self-administer the intranasal study drug (esketamine 28 mg, 56 mg, 84 mg, or placebo) at treatment sessions occurring twice a week for 4 weeks at the clinical site under clinical supervision. The first treatment session will be on Day 1. Responders (subjects who have $\geq 50\%$ reduction from baseline in MADRS total score) at the end of the double-blind induction phase will be eligible to proceed to the posttreatment phase; those who do not (ie, nonresponders) will proceed to the 4-week follow-up phase. Given the potential for treatment-emergent transient elevation in SBP and DBP, the guidance on Blood Pressure Monitoring should be followed on intranasal dosing days during the double-blind induction phase.

Posttreatment Phase

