Responders who completed the double-blind induction phase will enter the 24-week posttreatment phase to evaluate durability of efficacy after cessation of add-on intranasal esketamine or placebo treatment while continuing the oral antidepressant treatment regimen, as assessed by the time to relapse and proportion of responders and remitters at each visit in this phase. All subjects who are discontinued must be treated with an oral antidepressant after completion of the study, unless it is clinically inappropriate.

Open-label Induction Phase

Subjects who relapsed in the posttreatment phase will receive a 4-week open-label induction treatment course of intranasal esketamine. The beginning of the OL induction phase should be at least 2 weeks (14 calendar days) after the last dose in the double-blind induction phase. Subjects who meet the relapse criteria before 2 weeks after the last dose in the double-blind induction

phase will not have an option for joining open label induction phase. They will withdraw from the posttreatment phase and move forward to the follow up phase.

[figure not shown]
Subjects who enter the OL induction phase will start treatment sessions with 56 mg of intranasal esketamine on the first day of OL induction phase (Day 1 OL). On the fourth day (Day 4 OL), the dose will be increased to 84 mg. On Day 8 OL and Day 11 OL, the dose may remain the same as 84 mg or could be reduced by 28 mg as determined by the investigator based on efficacy and tolerability. On Day 15 OL, a dose reduction is permitted if required for tolerability; no dose increase is permitted on Day 15 OL. After Day 15 OL, the dose should be stable (unchanged). If needed for tolerability, a dose reduction is permitted from Day 15 OL until Day 25 OL.

The oral antidepressant medication initiated from the prospective lead-in phase, which will continue in the posttreatment phase will also be maintained throughout this phase.

Follow-up Phase

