2.6. Imputation Rules for Missing Adverse Event (AE) Dates

Treatment-emergent adverse events (TEAEs) are those events with an onset date/time on or after the start of study medication during induction phase (DB/OL), and occurred on or before the end of the corresponding induction phases (DB/OL). Adverse events (AEs) for the follow-up (DB/OL) phase are those events with an onset date on or after the start of the follow-up (DB/OL) phase, and occurred on or before the end of the follow-up (DB/OL) phase. Adverse events (AEs) for the posttreatment phase are those events with an onset date on or after the start of the posttreatment phase, and occurred on or before the end of the posttreatment phase. A conservative approach will be used to handle the missing dates for adverse events.

Onset Date

If the onset date of an AE is missing day only, it will be set to:

1. First day of the month that the AE occurred, if month/year of the onset of AE is different than the month/year of DB start date
2. The day of DB start date, if the month/year of the onset of AE is the same as month/year of the DB start date and month/year of the AE resolution date is different
3. The day of DB start date or day of AE resolution date, whichever is earliest, if month/year of the onset of AE and month/year of the DB start date and month/year of the AE resolution date are the same.

If the onset date of an AE is missing both day and month, it will be set to the earliest of:

1. January 1 of the year of onset, as long as this date is after the DB start date.
2. One day after the DB start date, if this date is the same year that the AE occurred.
3. The day of AE resolution date, if this date is the same year that the AE occurred.

A completely missing onset date of an adverse event will be set to the day of DB start date or day of AE resolution date, whichever is earliest.

Similar rules will be applied for OL missing onset date.

Resolution Date

The missing day of resolution of an AE will be set to the last day of the month of resolution.

If the resolution date of an AE is missing both day and month, it will be set to the earlier of the date of withdrawal, study completion, or December 31 of the year.

A completely missing resolution date of an AE that is not recorded as ongoing will be set to the date of study completion/discontinuation.

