5.1. Adverse Events

The Medical Dictionary for Regulatory Activities (MedDRA) (version 20.0 or above) will be used to classify adverse events (AEs) by system organ class and preferred term. Treatment-emergent adverse events (TEAEs) that occurred in each analysis phase (DB induction, DB follow-up, PT, OL induction, OL follow-up) will be summarized by system organ class and preferred term.

The number (%) of subjects with TEAEs, serious TEAEs (SAEs), and TEAEs that led to study drug discontinuation, dose reduction will be summarized by system organ class and preferred term. TEAEs will be summarized by onset time (4 week intervals). Data listings will be generated for deaths, other SAEs, and discontinuations due to AEs.

A TEAE is an event that is new in onset or increased in severity following treatment initiation. An event that starts prior to, and ends after the initiation of study medication will be considered treatment-emergent only if the severity increases after the start of medication.

Treatment-emergent adverse events (TEAEs) are defined as follows for each analysis phase:

- TEAEs in DB induction phase:
 - a. If AE onset time is not missing: DB start date/time \leq AE onset date and time \leq DB end date
 - b. If AE onset time is missing: DB start date \leq AE onset date \leq DB end date
- TEAEs in OL induction phase:
 - a. If AE onset time is not missing: OL start date/time \leq AE onset date and time \leq OL end date
 - b. If AE onset time is missing: OL start date \leq AE onset date \leq OL end date
- AEs in DB follow-up phase: DB FU start date \leq AE onset date \leq DB FU end date
- AEs in OL follow-up phase: OL FU start date \leq AE onset date \leq OL FU end date

- For the AEs that have both day and month missing, treatment-emergent flag is assigned based on the rules presented in Section 2.6.

In addition, TEAEs will be summarized by severity and relationship to study medication using the preferred term. For the summaries of TEAEs by severity/relationship to study medication, the observation with the most severe occurrence/closest relationship to study medication will be chosen if there is more than one incident of an AE reported during the analysis phase by the subject.

Adverse Events of Special Interest

Clinically relevant TEAEs of special interest will be examined separately grouped in the following categories:

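### Four-week onset intervals give effectively one bin in each 4-week induction phase, so adverse events without a per-session scale have no planned display over dosing sessions

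*SAP*

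**What the plan says.** SAP 5.1 plans TEAE tables by system organ class and preferred term, by severity and by relationship to study medication. It has one table on timing: "TEAEs will be summarized by onset time (4 week intervals"). No other AE table in that section is split by day, week or session. AE listings are planned only for deaths, other SAEs and discontinuations due to AEs.

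The phases in which intranasal drug is given are short. For the double-blind phase, SAP 1.2 says "The 4-week fixed dose double-blind induction phase will start on Day 1 and end at Day 28". For the open-label phase it says "Subjects who relapsed in the posttreatment phase will receive a 4-week open-label induction treatment course of intranasal esketamine". Dosing takes place "at treatment sessions occurring twice a week for 4 weeks at the clinical site", which Protocol Time and Events Schedules 1 and 3 place on Days 1, 4, 8, 11, 15, 18, 22 and 25 of each phase. SAP 2.6 ties the term TEAE to these phases: "Treatment-emergent adverse events (TEAEs) are those events with an onset date/time on or after the start of study medication during induction phase (DB/OL").

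The 84 mg arm does not start at 84 mg. Subjects receive 56 mg on Day 1, and Protocol 3.1 then says: "On Day 4 (Visit 3.3), the dose will be increased to 84 mg as a forced titration". The open-label course also starts at 56 mg: "On the fourth day (Day OL4), the dose will be increased to 84 mg".

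**The concern.** An onset table is meant to show when events begin relative to treatment. If the bin is as wide as the treatment phase, the table restates the overall incidence.

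Timing matters here for two reasons. First, in the 84 mg arm the Day 1 events occur under 56 mg and the later ones under 84 mg, and a single bin pools them under the arm label. Second, the protocol makes a time-course statement in its rationale for starting that arm lower. After noting that the largest CADSS effect came with the initial 84 mg dosing, Protocol 3.2.4 says: "However, on subsequent repeated dosing, dissociative symptoms lessen". A reader would want to know whether other acute effects behave in the same way.

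The events concerned are not rare. In the Phase 1 study of single doses (Protocol 1.1.2.1), the 15 Japanese subjects reported vertigo (46.7%), headache (26.7%), vomiting (26.7%) and nausea (20.0%). Dizziness, headache and nausea were also among the common events in the Japanese panel of the Phase 2 study (Protocol 1.1.2.3). Dizziness/vertigo and anxiety are AEs of special interest in SAP 5.1.

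**Working it through.** **Inputs.** Interval width: 4 weeks = 28 days (SAP 5.1). Double-blind phase: Day 1 to Day 28 (SAP 1.2). Open-label phase: 4 weeks (SAP 1.2). Dosing days: 1, 4, 8, 11, 15, 18, 22, 25, with a visit window of ±1 day after Day 1 (Protocol Time and Events Schedules 1 and 3). Intervals are counted from the first dose of each induction phase. SAP 5.1 does not state the origin, so this is an assumption.

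**Phase length.** 28 − 1 + 1 = 28 days = 4 weeks, which reproduces the plan's own figure.

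**Number of bins.** Bins = ceil(phase length / interval width) = ceil(28/28) = 1.

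**Bin of each dosing day.** Bin(d) = floor((d − 1)/28) + 1.
- Day 1: floor(0/28) + 1 = 1.
- Day 4: floor(3/28) + 1 = 1.
- Day 25, the last session: floor(24/28) + 1 = 1.
- Day 26, the last session given one day late: floor(25/28) + 1 = 1.

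All eight sessions are in bin 1.

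**Can a second bin appear?** Yes, but only as a tail. SAP 2.1.2 ends the phase at the later of the last visit and the completion or withdrawal date. A Day 28 visit held one day late reaches Day 29, and floor(28/28) + 1 = 2. A subject who discontinues on Day 27 and has the early-withdrawal visit 7 days later reaches Day 34, also bin 2. No scheduled dose falls there.

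**Where 4-week intervals do work.** The posttreatment phase lasts 24 weeks, and 24/4 = 6 bins. No intranasal drug is given in that phase. Each 4-week follow-up phase gives 4/4 = 1 bin.

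**Alternative widths in an induction phase.**

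| Rule | Bins | Bin of Days 1, 4, 8, 11, 15, 18, 22, 25 |
|---|---|---|
| 28 days (as planned) | 1 | 1, 1, 1, 1, 1, 1, 1, 1 |
| 14 days | 2 | 1, 1, 1, 1, 2, 2, 2, 2 |
| 7 days | 4 | 1, 1, 2, 2, 3, 3, 4, 4 |
| By dosing session (SAP Table 1 windows) | 8 | 1, 2, 3, 4, 5, 6, 7, 8 |

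Of these rules, only the session rule separates Day 1 from the Day 4 step.

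**What is already shown by dosing day.** Blood pressure and pulse (SAP 5.3), CADSS (5.5.2), BPRS+ (5.5.3) and MOAA/S (5.5.4). Dizziness/vertigo, nausea, vomiting, headache and anxiety have no counterpart. GAD-7 is taken only at baseline, Day 15 and Day 28 (SAP Table 1), so it cannot stand in for acute anxiety at a session.

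**The case against.** The strongest reply is that the time-course question, as the protocol raises it, is already answered. The statement in Protocol 3.2.4 rests on CADSS data, and CADSS is plotted for each dosing day. Psychosis-like effects, sedation, blood pressure and pulse also have by-session displays. This stands. A reader might infer from the single bin that the trial cannot show first-dose, dose-step or attenuation effects. The documents do not support that for any of these effects.

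A reader might also infer that the protocol expects tolerability in general to improve with repetition. It says so only for dissociation, given as an example. Protocol 1.1.2.3 says that blood pressure changes do not appear to attenuate. Likewise, the call in Protocol 1.2 for careful assessment of 84 mg concerns fixed dosing over 4 weeks. Whole-phase incidence by arm addresses that, so it is not a request for onset by session.

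Three further points hold. Intolerability leading to discontinuation is tabulated and listed (SAP 5.1), and exposure is shown in bands of 7 days or less, 8–14, 15–21, 22–25 and over 25 days, with the number of sessions (SAP 3.3). SAP 5.1 uses TEAE for events in every analysis phase, so the 4-week rule is not empty throughout the study. And AE onset dates and times are recorded, so the information is left out of a table but not lost.

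What the reply does not reach is the group of common events with no per-session scale. For these the onset table is the only planned AE display of timing, and the listings in SAP 5.1 are too narrow for a reader to rebuild it.

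**Conclusion.** The point holds in a limited form. In each induction phase eight sessions collapse to effectively one bin, so the planned onset table adds nothing to overall TEAE incidence there. The consequence is confined to AEs without a per-session scale. For these, no planned AE table separates the 84 mg arm's 56 mg session on Day 1 from its 84 mg sessions from Day 4, or shows change with repetition.

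This is a minor reporting matter. It affects no endpoint, test, analysis set, data collection or safety monitoring, and leaves the primary analysis untouched.

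The conclusion assumes that intervals run from the first dose of each induction phase. If they ran from study Day 1, the double-blind result would be the same. An open-label course could then straddle a boundary, but at a point set by the date of relapse and not by dosing, which would be no more informative.

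**What to change.** In SAP 5.1, for the DB and OL induction phases, replace the 4-week intervals with onset by dosing session. Use the dosing-day windows already in SAP Table 1 (Day 1, 2–6, 7–9, 10–13, 14–16, 17–20, 21–23, 24 to end of phase), with the subjects dosed at that session as denominator. Keep 4-week intervals for the posttreatment phase. Do not use plain weekly bins.

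Two details need a sentence each. The Table 1 windows open before the target day, so an event that starts inside a window but before that session's dose should count to the preceding session. Otherwise a Day 2 event after 56 mg would appear under the Day 4 session. Also, SAP 2.7 sets a missing onset time after the first day to 00:00, which would place an event on a dosing day before the dose. The table should count such an event to that day's session.

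The cost is a short SAP edit and a longer table. Onset dates and times and the windows already exist, and nothing changes in trial conduct or in the error rate.

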During the Phase 1 Study ESKETINTRD1002, 15 healthy Japanese and 14 healthy Caucasian subjects received single intranasal doses of esketamine 28 mg, 56 mg, and 84 mg in a crossover manner.¹³ The mean body mass index (BMI) were 21.98 kg/m² and 23.49 kg/m² in Japanese and Caucasian subjects, respectively. On average, plasma esketamine C_{max} and AUC values were up to 48% higher in Japanese subjects compared with Caucasian subjects. The incidence of the treatment-emergent adverse events (TEAEs) was higher in Japanese subjects (80% [12/15]) as compared to Caucasian subjects (50% [7/14]). The most commonly reported TEAEs by preferred term (>10%) in Japanese subjects were headache (26.7% [4/15] of subjects), vertigo (46.7% [7/15] of subjects), vomiting (26.7% [4/15] of subjects), derealization (20.0% [3/15] of subjects), nausea (20.0% [3/15] of subjects), depressed level of consciousness (13.3% [2/15] of subjects), somnolence (13.3% [2/15] of subjects), and confusional state (13.3% [2/15] of subjects). Though TEAEs were seen in majority of subjects, they were transient, mild or moderate in severity and were consistent with previously reported TEAEs for esketamine. Hence, a single intranasal dose of esketamine (28 mg, 56 mg, and 84 mg) was observed to be safe and well tolerated in Japanese subjects with no new safety findings of clinical concern.

Study ESKETINTRD1003 compared the PK, safety, and tolerability of intranasally administered esketamine in healthy elderly (≥ 65 years of age) and younger adult subjects (18 to 55 years of age, both inclusive).¹⁴ Subjects received a single intranasal treatment of esketamine 28 mg. Median time to reach the maximum plasma concentration (t_{max}) of esketamine was approximately 30 minutes for both age groups. The geometric means of the C_{max} and area under the plasma concentration-time curve from time 0 to infinite time, AUC_{∞} , for esketamine were approximately 21% and 17% higher, respectively, in the elderly compared with younger adult subjects.¹⁴

Another Study, ESKETINTRD1012, compared the PK, safety, and tolerability of intranasally administered esketamine in elderly subjects (≥ 75 years of age) and healthy younger adult

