In a 1-year longitudinal study, 150 subjects were divided into 5 groups of 30 subjects each. Frequent ketamine users (more than 4 times per week), infrequent ketamine users (at least once a month), abstinent users (abstinent for at least 1 month), polydrug controls, and non-users of illicit drugs.⁴³ Eighty percent of the participants were retested at the end of 1 year. Cognitive deficits (including impairment in spatial working memory, pattern recognition memory and category fluency) were mainly observed in frequent users and not with the infrequent users. Short-lasting, dose-dependent effects of psychosis were associated with ketamine users. There was no increase in symptoms over time, and symptoms were completely reversible upon stopping use of ketamine. As noted, these data should be interpreted with caution, as baseline data predating drug use were not available. Furthermore, in their recent review, Morgan and Curran report that there is little evidence of any link between chronic, heavy use of ketamine and diagnosis of a psychotic disorder.⁴²

The principal action of ketamine is at the NMDA receptor, and the consequences of ketamine use on cognition have been fairly widely investigated. Several studies have examined cognitive function in infrequent and frequent ketamine users.^{42,43} Overall, infrequent or recreational ketamine use does not appear to be associated with long-term cognitive impairment.⁴³ The most robust

findings are that frequent ketamine users (more than 5 times a week) exhibit impairments in both short- and long-term memory.⁴¹ Although dosages have varied, dosages reported by ketamine users in this study were much higher than the dosages of ketamine or equivalent doses of esketamine intended for use in treating TRD. Memory impairments may be reversible when individuals stop using the drug, as they were not found in a group of 30 ex-ketamine users who had been abstinent for at least a year.^{42, 43}

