- Suggestive of abuse potential (Aggression, Confusional state, Decreased activity, Dependence, Disorientation, Dissociation, Dissociative disorder, Dizziness, Drug abuse, Drug abuser, Drug dependence, Drug use disorder, Drug detoxification, Drug diversion, Drug rehabilitation, Drug tolerance, Drug tolerance increased, Drug withdrawal convulsions, Drug withdrawal headache, Drug withdrawal syndrome, Euphoric mood, Feeling abnormal, Feeling drunk, Feeling of relaxation, Hallucination, Hallucination, auditory, Hallucination, gustatory, Hallucination, olfactory, Hallucination, synaesthetic, Hallucination, tactile, Hallucination, visual, Hallucinations, mixed, Inappropriate affect, Mental impairment, Product tampering, Psychomotor hyperactivity, Psychotic disorder, Rebound effect, Somatic hallucination, Somnolence, Substance abuser, Substance dependence, Substance use, Substance use disorder, Substance-induced mood disorder, Substance-induced psychotic disorder, Thinking abnormal, Withdrawal arrhythmia, Withdrawal syndrome)
- increased blood pressure (Blood pressure increased, Blood pressure diastolic increased, Blood pressure systolic increased, Hypertensive crisis, Hypertensive emergency, Hypertension)
- increased heart rate (Heart rate increased, Tachycardia, Extrasystoles)
- transient dizziness/vertigo (Dizziness, Dizziness exertional, Dizziness postural, Procedural Dizziness, Vertigo, Vertigo labyrinthine, Vertigo positional, Vertigo CNS origin);
- impaired cognition (Cognitive disorder);
- cystitis (Allergic cystitis, Chemical cystitis, Cystitis, Cystitis erosive, Cystitis haemorrhagic, Cystitis interstitial, Cystitis noninfective, Cystitis ulcerative, Cystitis-like symptom, Pollakiuria, Dysuria, Micturition urgency, Nocturia);
- anxiety (Anticipatory anxiety, Anxiety, Anxiety disorder, Agitation, Fear, Feeling jittery, Irritability, Nervousness, Panic attack, Tension).

The number and percentage of subjects taking concomitant medication for dissociation events (preferred term of Dissociation) at any time during each induction phase will be provided.

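### The impaired-cognition group of special-interest events holds a single preferred term, so its row is likely to understate cognitive events

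*SAP*

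**What the plan says.** Protocol 3.2.6 lists impaired cognition among the categories of special interest that are to be examined separately. Protocol 11.8 defers the detailed list to the SAP.

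SAP 5.1 gives the category as "impaired cognition (Cognitive disorder", and the parenthesis closes after that one term. Related terms are listed under a different category: "Suggestive of abuse potential (Aggression, Confusional state, Decreased activity, Dependence, Disorientation, Dissociation, Dissociative disorder, Dizziness" and, further along the same list, "Inappropriate affect, Mental impairment, Product tampering" and "Thinking abnormal, Withdrawal arrhythmia, Withdrawal syndrome".

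SAP 5.1 also lets one term serve two categories. Dizziness is in the abuse-potential list and again in "transient dizziness/vertigo (Dizziness, Dizziness exertional, Dizziness postural".

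Outside the special-interest groups, SAP 5.1 says that events "will be summarized by system organ class and preferred term".

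On background, Protocol 1.1.2.3 reports that "frequent ketamine users (more than 5 times a week) exhibit impairments in both short- and long-term memory". Protocol 1.1.2.1 reports, for healthy Japanese subjects in the Phase 1 comparison with Caucasian subjects, "confusional state (13.3% [2/15] of subjects".

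**The concern.** A special-interest category exists to gather related preferred terms, so that a signal spread over several of them can be seen in one count of subjects. A category with one term does not do this; it repeats one row of the general adverse event table under a broader label. A reader who turns to impaired cognition to learn how many subjects had a cognitive event will get the number coded to Cognitive disorder and nothing else.

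Adverse event reporting matters more here because I find no cognitive test in the three Time and Events Schedules. The Hopkins Verbal Learning Test-Revised appears only in the protocol's abbreviation list. At stake is how one named safety interest is presented. No hypothesis test or decision rule uses this category.

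**Working it through.** The plan states no event rate or power figure for this category, so the check is a count of the SAP 5.1 lists and a lookup of terms.

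**Step 1. Terms per category in SAP 5.1**

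| Category | Preferred terms listed |
|---|---|
| Suggestive of abuse potential | 49 |
| Cystitis | 13 |
| Anxiety | 10 |
| Transient dizziness/vertigo | 8 |
| Increased blood pressure | 6 |
| Increased heart rate | 3 |
| Impaired cognition | 1 |

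The cystitis group reaches down to symptoms such as Dysuria and Nocturia. The cognition group has no symptom-level term.

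**Step 2. Where each cognitive term is found**

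| Term | Category |
|---|---|
| Cognitive disorder | Impaired cognition |
| Confusional state | Abuse potential only |
| Disorientation | Abuse potential only |
| Mental impairment | Abuse potential only |
| Thinking abnormal | Abuse potential only |
| Memory impairment, Amnesia | None |
| Dizziness (check on double listing) | Abuse potential and dizziness/vertigo |

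**Step 3. Direction of the effect.** Let N(G) be the number of subjects with at least one event coded to a term in group G. Let G1 = {Cognitive disorder}, and let G2 be G1 plus the added terms. Since G1 is contained in G2, N(G1) ≤ N(G2). The difference is the number of subjects who have an event among the added terms but none coded to Cognitive disorder. It cannot be negative, and it is zero only if there are no such subjects.

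**Step 4. Can a reader recover N(G2) from the other tables?** Only within bounds. One subject may have events under several terms, so separate preferred-term counts n1, n2, ... give max(ni) ≤ N(G2) ≤ sum(ni). The abuse-potential total does not help either. It mixes the four terms with Somnolence, Dizziness, Feeling abnormal and Dissociation, and Protocol 1.1.2.3 names all four of these among events reaching at least 10% in some treatment group of the Japanese panel (Panel B) of ESKETINTRD2003.

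**Step 5. The one relevant rate in the documents.** For confusional state, 2/15 = 13.3%, which reproduces the protocol's figure. The exact (Clopper-Pearson) 95% interval is 1.7% to 40.5%. The documents give no rate for Cognitive disorder and none for memory events in esketamine trials, so the difference in Step 3 has a known direction but no estimable size.

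**The case against.** The strongest reply is that nothing disappears. Four of the terms are already special-interest events, under abuse potential, and every event, including any memory or attention event, is tabulated by system organ class and preferred term. That stands. A reader might infer that these events never count; they fail to count only in the impaired-cognition row. What remains is that no table gives the number of subjects with any cognitive event, and that memory events belong to no special-interest category.

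Second, the grouping is a judgement the SAP was entitled to make. Its amendment history says the list was aligned with the global Phase 3 trials, and no passage says that transient confusion after dosing must be called cognitive. This is fair, and it is the reason to keep the existing one-term row. It does not justify having no broader row beside it.

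Third, the memory finding should not be pressed too far. It concerns very frequent ketamine users. The same part of Protocol 1.1.2.3 says that infrequent or recreational use does not appear to carry long-term cognitive impairment, and that the users' dosages were much higher than those intended in treatment-resistant depression. It shows that memory is a known cognitive concern for this drug class, not that memory events are expected here. Nor do the documents tie the up to 48% higher exposure in Japanese subjects to cognition.

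Fourth, acute effects are measured by other instruments. The CADSS has an amnesia component (SAP 5.5.2) and the MOAA/S measures sedation (SAP 5.5.4). Both are taken around dosing (the CADSS predose, at 40 minutes and at 1.5 hours), so neither covers cognition between sessions.

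**Conclusion.** The point holds as one of safety presentation. With a single term, the impaired-cognition row is likely to understate cognitive events. The direction follows from the lists themselves; the word likely rests on the assumption that some subjects will have confusion, disorientation, memory or attention events that are not also coded to Cognitive disorder.

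Two stronger readings are tempting and are not supported. One is that the row will read near zero. The documents give no rate for Cognitive disorder, so this would be a guess about coding practice. The other is to multiply 2/15 by the 37 subjects planned per esketamine arm and say that about five (0.133 × 37 = 4.9) would be missed in each. The 2/15 comes from healthy subjects who took single doses of 28, 56 and 84 mg in a crossover, so it does not belong to any one dose. Its interval alone spans 0.0166 × 37 = 0.6 to 0.405 × 37 = 15 subjects. Confusional state is also absent from the list of events reaching 10% in Panel B, whose subjects had treatment-resistant depression, although that panel was small and had no 28 mg or 84 mg arm. Any such subjects would in any case be reported under abuse potential and in the general table.

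The primary analysis, alpha, power and sample size are untouched.

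**What to change.** Before unblinding, amend the term list in SAP 5.1:

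- List Confusional state, Disorientation, Mental impairment and Thinking abnormal under impaired cognition as well as under abuse potential. Dizziness is already treated in this way.
- Add named memory and attention preferred terms, for example Memory impairment, Amnesia and Disturbance in attention, checked against the MedDRA version in use.
- Report the number of subjects with at least one event in the enlarged group, and keep Cognitive disorder as a separate row so that comparison with the global studies is preserved.

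The cost is one revised list and its table program. The downside is overlap between categories and a higher descriptive count, so a footnote should say that a subject may appear in more than one category and that category totals must not be added.
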